	
than start date of administration of concomitant drug, the data should be excluded from aggregation of concomitant drugs. If date cannot be complemented by above rules or the order of start date and last date of administration of concomitant drug is reversed, the data should be included in aggregation of concomitant drugs.
 
② Data with description about “Previously used drug”
 
 
• If there is clear description in start date of administration of previously used drug with year and month, “date” is complemented by “1”.
 
• If there is clear description in start date of administration of previously used drug with year, “month” and “date” each is complemented by “1”.
 
• If last date of administration of previously used drug is earlier than start date of the initial administration of this drug, the data should be included in aggregation of concomitant drugs. If date cannot be complemented by above rules, last date of administration of previously used drug is deemed as unknown and it is not handled as concomitant drug.
 
 
② Data with description about “Administration status of antituberculosis drug”
 
 
• If there is clear description in start date of administration of antituberculosis drug with year and month, “date” is complemented by “1”.
 
• If there is clear description in start date of administration of antituberculosis drug with year, “month” and “date” each is complemented by “1”.
 
• If there is clear description in last date of administration of antituberculosis drug with year and month, “date” is complemented by the end day of the month.
 
• If there is clear description in last date of administration of antituberculosis drug with year, “month” and “date” are complemented by [12] and [31], respectively.
 
• If last date of administration of antituberculosis drug is earlier than start date of the initial administration of this drug and last date of the final administration of this drug is earlier than start date of administration of antituberculosis drug, the data should be excluded from aggregation of concomitant drugs. If date cannot be complemented by above rules or the order of start date and last date of administration of antituberculosis drug is reversed, the data should be included in aggregation of concomitant drugs.
 
 
(A term, “clear” means a situation where there is no ambiguous description such as “around” or “middle of month” and only numerical value is described)

Presence or absence of	Based on “161206 drug list addition (Fix)CRO”, if there is a data

Name of data	Derivation and calculation method
use of concomitant drug (aminosalicylic acid preparation)	on concomitant drug corresponding to relevant drug code, patients are deemed to concomitantly received aminosalicylic acid preparation and in any other situations, patients are deemed not to concomitantly receive aminosalicylic acid preparation.
Presence or absence of use of concomitant drug (steroid)	Based on “161206 drug list_addition (Fix)CRO”, if there is a data on concomitant drug corresponding to relevant drug code, patients are deemed to concomitantly receive steroid and in any other situations, patients are deemed not to concomitantly receive steroid.
Presence or absence of concomitant drug (immunosuppressive drug)	Based on “161206 drug list_addition (Fix)CRO”, if there is a data on concomitant drug corresponding to relevant drug code, patients are deemed to concomitantly received immunosuppressive drug and in any other situations, patients are deemed not to concomitantly receive immunosuppressive drug.
Presence or absence of concomitant drug (immunomodulative drug)	Based on “161206 drug list_addition (Fix)CRO”, if there is a data on concomitant drug corresponding to relevant drug code, patients are deemed to concomitantly receive immunomodulative drug and in any other situations, patients are deemed not to concomitantly receive immunomodulative drug.
Presence or absence of concomitant drug (enteral nutrient)	Based on “161206 drug list_addition (Fix)CRO”, if there is a data on concomitant drug corresponding to relevant drug code, patients are deemed to concomitantly received enteral nutrient and in any other situations, patients are deemed not to concomitantly receive enteral nutrient.
Presence or absence of concomitant drug (colchicine)	Based on “161206 drug list_addition (Fix)CRO”, if there is a data on concomitant drug corresponding to relevant drug code, patients are deemed to concomitantly received colchicine and in any other situations, patients are deemed not to concomitantly receive colchicine.
Presence or absence of concomitant drug (Others)	If there is data with descriptions about concomitant drug other than immunosuppressive drug, immunomodulative drug, enteral nutrient, and colchicine, patients are deemed to have use of other concomitant drug, and in any other situations, patients are deemed to have no concomitant drug.
Presence or absence of combination therapy	
Data including descriptions in “combination therapy” in the survey sheet obtained between the start date of the initial administration and the last date of the final administration of this drug should be applicable.
 
Even if the start date or last date of combination therapy is not identified, the data should be applicable. (the data should be excluded only if the administration period is not obviously overlapped with that of this drug)
 
Patients with description about combination therapy are deemed to receive combination therapy. If there is no description in “treatment except for drug treatment/presence or absence of combination therapy” and whether patients receive combination therapy or not cannot be assessed, whether patients receive combination therapy is deemed to be unknown/not described, and in any other situations, patients are deemed to receive no

Name of data	Derivation and calculation method
	combination therapy.
Presence or absence of combination therapy (operation/others)	
If there is a check mark in a box for operation in name of treatment except for drug treatment/therapy in “treatment except for drug treatment/combination therapy for gastro-intestinal Behcet disease (including operation)” and there is description corresponding to operation as combination therapy in “[HUMIRA BD] converted data for provision for analysis”, combination therapy provided in the patients is deemed to be operation, and there is data about other therapy than operation, the patients are deemed to receive other combination therapy.
 
If there is data corresponding to operation, patients are deemed to have received operation, and in any other situations, patients are deemed to have not undergone operation.
 
If there is data corresponding to others, patients are deemed to receive other combination therapy, and in any other situations, patients are deemed not to receive combination therapy.

Presence or absence of implementation of endoscopy	
If at least one description of date between the start date of the initial administration of this drug and the last date of the final administration of this drug in implementation date of endoscopy in “level of improvement in endoscopy findings” in the survey sheet, endoscopy is deemed to have been implemented. If there is a check mark in a box for not implemented, endoscopy is deemed to have not been implemented. In any other situations, whether endoscopy has been implemented or not is deemed to be unknown/not described.
 
The site of endoscopy should be derived from data with check mark in “site of ulcer with the maximum diameter” in the survey sheet.

Presence or absence of drug used after discontinuation of administration of this drug	
If there is data with description in “drugs used after discontinuation of administration of this drug”, patients are deemed to have drugs after discontinuation of administration of this drug. If there is data about drugs used after discontinuation, patients are deemed to have drugs used after discontinuation of administration of this drug. If whether patients have drugs used after the discontinuation of administration of this drug or not is not described or cannot be assessed, presence or absence of drug used after the discontinuation of this drug is deemed to be unknown/not described, and in any other situations, patients are deemed to have no drug used after the discontinuation of administration of this drug.

Presence or absence of use of drug used after the discontinuation of administration of this drug (aminosalicylic acid preparation)	
If there is data about aminosalicylic acid preparation in “drugs used after the discontinuation of this drug” in the survey sheet, patients are deemed to have received aminosalicylic acid preparation, and in any other situations, patients are deemed to have not received aminosalicylic acid preparation.

Presence or absence of use of concomitant drug (steroid)	
If there is data with description in steroid in “drugs used after the discontinuation of this drug” in the survey sheet, patients are deemed to have received steroid, and in any other situations,

Name of data	Derivation and calculation method
	patients are deemed to have not received steroid.
Presence or absence of drugs used after the discontinuation of this drug (immunomodulative drug)	If there is data with description in immunomodulative drug in “drugs used after the discontinuation of this drug” in the survey sheet, patients are deemed to have received immunomodulative drug, and in any other situations, patients are deemed to have not received immunomodulative drug.
Presence or absence of drugs used after the discontinuation of this drug (antibiotic)	If there is data about antibiotic in “drugs used after the discontinuation of this drug” in the survey sheet, patients are deemed to have received antibiotic, and in any other situations, patients are deemed to have not received antibiotic.
Presence or absence of drugs used after the discontinuation of this drug (biological preparation)	If there is data with description in biological preparation in “drugs used after the discontinuation of this drug” in the survey sheet, patients are deemed to have received biological preparation, and in any other situations, patients are deemed to have not received biological preparation.
Presence or absence of drugs used after the discontinuation of this drug (other drug)	If there is data about other drugs in “drugs used after the discontinuation of this drug” in the survey sheet, patients are deemed to have received other drug, and in any other situations, patients are deemed to have not received other drug after the discontinuation of administration of this drug.
Main symptoms of Behcet's disease: presence or absence of recurrent oral mucosa aphthous ulcer	If there is a check mark in “1,2,3” in “recurrent oral mucosa aphthous ulcer” at the start of administration of this drug in survey sheet with the date before the start date of the initial administration of this drug, mucosal aphthous ulcer is deemed to be present, and in any other situations, it is deemed to be absent.
Main symptoms of Behcet's disease: presence or absence of cutaneous symptoms	If there is a check mark in “1,2,3” in “cutaneous symptoms” at the start of administration of this drug in survey sheet with the date before the start date of the initial administration of this drug, cutaneous symptoms is deemed to be present, and in any other situations, cutaneous symptom is deemed to be absent.
Main symptoms of Behcet's disease: presence or absence of eye symptoms	If there is a check mark in “1,2,3” in “eye symptoms” at the start of administration of this drug in survey sheet with the date before the start date of the initial administration of this drug, eye symptoms is deemed to be present, and in any other situations, it is deemed to be absent.
Main symptoms of Behcet's disease: presence or absence of ulcer of vulva	If there is a check mark in “1,2,3” in “ulcer of vulva” at the start of administration of this drug in survey sheet with the date before the start date of the initial administration of this drug, ulcer of vulva is deemed to be present, and in any other situations, it is deemed to be absent.
Main symptoms of Behcet's disease: presence or absence of arthritis without deformity or rigidity	If there is a check mark in “1,2,3” in “arthritis without deformity” at the start of administration of this drug in survey sheet with the date before the start date of the initial administration of this drug, arthritis without deformity is deemed to be present, and in any other situations, it is deemed to be absent.
Accessory symptoms of Behcet's disease: presence or absence of	If there is a check mark in “epididymitis” at the start of administration of this drug in survey sheet with the date before the start date of the initial administration of this drug,

Name of data	Derivation and calculation method
epididymitis	epididymitis is deemed to be present, and in any other situations, it is deemed to be absent.
Accessory symptoms of Behcet's disease: presence or absence of vascular lesion	If there is a check mark in “vascular lesion” at the start of administration of this drug in survey sheet with the date before the start date of the initial administration of this drug, vascular lesion is deemed to be present, and in any other situations, it is deemed to be absent.
Accessory symptoms of Behcet's disease: presence or absence of moderate or higher degree central nervous lesion	If there is a check mark in “moderate or higher degree central nervous lesion” at the start of administration of this drug in survey sheet with the date before the start date of the initial administration of this drug, moderate or higher degree central nervous lesion is deemed to be present, and in any other situations, it is deemed to be absent.
Test for tuberculosis	Test was implemented: If “test for tuberculosis or IGRA test” were implemented and “chest X-ray or CT scanning” was implemented. Tests were not implemented: Other than above situations
Test of hepatitis B	Test was implemented: If “HBV-DNA quantitative test” was implemented or patients are negative for “Hbs antigen test”, “Hbs antibody test”, and “Hbc antibody test”. Tests were not implemented: Other than above situations
Responding patients	Patients who were assessed to have obtained “improvement” and “significant improvement” as level of overall improvement are defined as responding patients.

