Presence or absence of drug used for previously used drug (antibiotic)	Based on “161206 drug list_addtion (Fix)CRO”, if there is a data on previously used drug corresponding to relevant drug code or there is a check mark in a box for antibiotic in the survey sheet, patients are deemed to have previously received antibiotic and in any other situations, patients are deemed not to receive antibiotic.
Presence or absence of previously used drug (other drug)	Based on “161206 drug list_addtion (Fix)CRO”, if there is a data on “Other drugs than biological preparations” in the survey sheet and any data on previously used drug except for aminosalicylic acid preparation, steroid, immunomodulative drug, or antibiotic, patients are deemed to have previously received other drugs and in any other situations, patients are deemed not to have received other drugs.
Presence or absence of drug used for previously used drug (adalimumab)	Based on “161206 drug list_addtion (Fix)CRO”, if there is a data on previously used drug corresponding to relevant drug code, patients are deemed to have previously received adalimumab and in any other situations, patients are deemed not to have received adalimumab.
Presence or absence of previously used drug (infliximab)	Based on “161206 drug list_addtion (Fix)CRO”, if there is a data on previously used drug corresponding to relevant drug code, patients are deemed to receive infliximab and in any other situations, patients are deemed not to have previously received infliximab.
Presence or absence of previously used drug (other biological preparations)	Based on “161206 drug list_addtion (Fix)CRO”, if there is a data on “Biological preparations” in the survey sheet and any data on previously used drug except for adalimumab or infliximab, patients are deemed to have previously received other biological preparations and in any other situations, patients are deemed not to have previously received other biological preparations.

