Presence or absence of previous treatment	Of data in which there are any descriptions about “previously used drug/previous treatment for gastro-intestinal Behcet disease”, data excluding that about previously used drug is deemed to be previous treatment. Patients with description about previous treatment is deemed as patients who received previous treatment. If there is no description in “previously used drug/previous treatment for gastro-intestinal Behcet disease” and whether previous treatment is present or not cannot be assessed, previous treatment is deemed to be unknown/not described, and

Name of data	Derivation and calculation method
	in any other situations, patients are deemed to have received no previous treatment.
Presence or absence of previous treatment (operation/others)	
If there is a check mark in a box for operation in “previously used drug/previous treatment for gastro-intestinal Behcet disease” and description corresponding to operation in “[HUMIRA BD] converted data for provision for analysis”, previous treatment is deemed to be operation, and in any other situations, it is deemed to be others.
 
If there is a data corresponding to operation, patients are deemed to have undergone operation, and in any other situations, patients are deemed to have not undergone operation.
 
If there is a data corresponding to others, patients are deemed to have received other previous treatment, and in any other situations, patients are deemed to have not received previous treatment.

Presence or absence of previously used drug/previous treatment	If data corresponds to presence or absence of previously used drug and previous treatment, patients are deemed to have previously used drug or have received previous treatment. Whether previously used drug or previous treatment is present or not is “unknown/not described”, “unknown/not described” should be described for presence or absence of previously used drug/previous treatment, and in any other situations, “none” should be described.

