Detailed classifications of medical history	tuberculosis, bacterial bronchitis, nontuberculous mycobacterial infection, aplastic anaemia, pancytopenia, malignant tumour, others
Previously used drug/previous treatment	Absent, present, unknown, not described
Classification of biological preparation as previously used drug/previous treatment	Adalimumab, infliximab, others
Classification of drugs other than biological preparation as previously used drug/previous treatment	Biological preparation, aminosalicylic acid preparation, steroid, immunomodulative drug, antibiotic, other previously used drug, operation, other previous treatment
Concomitant drug	Absent, present, unknown, not described
Detailed classification of concomitant drugs	Aminosalicylic acid preparation, oral adrenocortical steroid, immunomodulative drug, immunosuppressive drug, enteral nutrient, colchicine, others
Combination therapy	Absent, present, unknown, not described
Detailed classification of combination therapy	Operation, others
Endoscopy	Absent, present, unknown, not described

data	Method of dividing hierarchy
Detailed classifications of endoscopy	Ileocecum, colon, esophagus, others
Level of improvement in endoscopy findings	Remission or scar, shrinkage, no change, aggravation, not assessed
Evaluation of gastrointestinal symptoms	
0,1,2,3,4
 
0: No symptom
 
1: There was symptom in last 2 weeks but daily living activities were rarely disturbed.
 
2: There was symptom in last 2 weeks and daily living activities were slightly disturbed.
 
3: There was symptom in last 2 weeks and daily living activities were disturbed.
 
4: There was symptom in last 2 weeks and daily living activities were severely disturbed.

Detailed classifications of gastrointestinal symptoms	Abdominal pain, diarrhoea, others (including bloating, abdominal tenderness, haemorrhage)
Self-administration	Absent, present
Self-administration error	Absent, present, unknown, not described
Drug used after the discontinuation of this drug	Absent, present, unknown, not described
Detailed classifications of drug used after the discontinuation of this drug	Aminosalicylic acid preparation, steroid, immunomodulative drug, biological preparation, other drug
Level of overall improvement	Significant improvement, improvement, ineffective
Detailed classifications of level of overall improvement for patients with improvement or higher level of improvement	Significant improvement, improvement

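### The rule for 'Others' among concomitant drugs omits two named classes, so aminosalicylate and steroid users are also counted as 'Others' in Table 1.12.1

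*SAP*

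**What the plan says.** SAP section 10.1 has a row for each of six concomitant classes, derived from the drug code list. Patients without a matching code fall to the negative side, for example "patients are deemed not to concomitantly receive aminosalicylic acid preparation" and "patients are deemed not to concomitantly receive steroid". The residual row then applies to any "concomitant drug other than immunosuppressive drug, immunomodulative drug, enteral nutrient, and colchicine, patients are deemed to have use of other concomitant drug". It ends by treating all remaining patients as having no concomitant drug.

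Section 11 sets the classes for tabulation as "Aminosalicylic acid preparation, oral adrenocortical steroid, immunomodulative drug, immunosuppressive drug, enteral nutrient, colchicine, others".

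The parallel residual row in 10.1 for previously used drugs is complete for its non-biologic classes: it takes "any data on previously used drug except for aminosalicylic acid preparation, steroid, immunomodulative drug, or antibiotic".

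On surgery, the 10.1 row for previous treatment asks for a ticked operation box "and description corresponding to operation in" the converted data file, "and in any other situations, it is deemed to be others". The row for combination therapy asks for the ticked box "and there is description corresponding to operation as combination therapy in" the same file.

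Section 13.1 reports all these classes in Table 1.12.1 for three populations: safety, efficacy, and patients with fixed survey sheets.

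**The concern.** A residual class should hold what no named class holds. Here the derivation in 10.1 and the class list in 11 disagree on what 'Others' contains. A programmer who follows 10.1 will place each aminosalicylate and steroid record in two classes. Table 1.12.1 describes background treatment in an all-case survey of patients who did not respond to existing treatment, and section 3.1 says results feed regulatory reporting and the reassessment application. A reader of the 'Others' row would take it as use of drugs outside the six classes, and it would not be that.

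The operation rows raise a smaller question of the same kind. If both sources are required, an operation recorded in only one of them is not counted as an operation.

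**Working it through.** **Class by class (SAP 10.1 against 11)**

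| Class | Own row in 10.1 | Separate from 'others' in 11 | Excluded from 'Others' in 10.1 |
|---|---|---|---|
| Aminosalicylate | yes | yes | **no** |
| Steroid | yes | yes (labelled oral) | **no** |
| Immunosuppressive | yes | yes | yes |
| Immunomodulative | yes | yes | yes |
| Enteral nutrient | yes | yes | yes |
| Colchicine | yes | yes | yes |

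**How often the flag differs, as logic.** Six named classes plus a truly other drug give 2^7 − 1 = 127 non-empty combinations. The 10.1 flag and a flag with all six exclusions differ when there is an aminosalicylate and/or steroid (3 ways), no truly other drug (1 way) and any mix of the remaining four classes (2^4 = 16 ways): 3 × 16 = 48 combinations. In all 48 the 10.1 rule says present and the section 11 list says absent. The error never runs the other way.

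**Size.** Table 1.12.1 takes breakdown rates over patients at the next higher level, here concomitant-drug users. Among them let a be the share on an aminosalicylate or steroid, and o the share on a truly other drug. The reported 'Others' share is the share on either, so it cannot be below a. If the two are independent, it is 1 − (1 − a)(1 − o). Without that assumption, the excess over o lies between max(0, a − o) and min(a, 1 − o). The SAP gives neither a nor o, so the values below are assumptions.

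| a | o | Reported if independent | Excess if independent | Possible excess |
|---|---|---|---|---|
| 60% | 20% | 1 − 0.4 × 0.8 = 68% | 48 points | 40 to 60 |
| 30% | 20% | 1 − 0.7 × 0.8 = 44% | 24 points | 10 to 30 |
| 60% | 80% | 1 − 0.4 × 0.2 = 92% | 12 points | 0 to 20 |
| 30% | 80% | 1 − 0.7 × 0.2 = 86% | 6 points | 0 to 20 |

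The excess is large if few patients take truly other drugs and small if most do.

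**What is not touched.** The any-concomitant-drug row and the six named rows have their own rules. Concomitant 'Others' and operation are not among the factors listed for Tables 2.9 and 3.4.

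**Closing wording of the row.** A patient on colchicine alone has a concomitant drug under the general rule in 10.1, yet the residual row would call that patient free of concomitant drugs.

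**Operation rows.** With two sources there are four cases: both, box only, converted entry only, neither. 'And' and 'or' agree on the first and last and differ on the two single-source cases. For previous treatment, 'and' sends both of these to others. For combination therapy they fail the operation test and may land in neither class, because 'other' there needs data on a therapy that is not an operation. The loss equals the share of operations recorded in one source only. The SAP does not state it, and it may be anything from none upward.

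**The case against.** **The overlap note.** The notes to Table 1.12.1 allow the concomitant classes to overlap. That covers a patient who takes drugs from several classes. It does not make one aminosalicylate record also an 'other' drug.

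**The table cites section 11.** Table 1.12.1 refers to the section 11 classes, which are correct. That makes this an inconsistency between sections, but 10.1 is where the flag is derived, and nothing tells the programmer to override it.

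**The steroid label.** Section 11 says oral steroid and 10.1 says steroid, so some non-oral steroids might be meant for 'Others'. That could explain non-oral steroids at most; it explains neither oral steroids nor aminosalicylates. The point does stand against a careless fix: if the named class is oral only, excluding every steroid from 'Others' would leave non-oral steroids in no class.

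**Stronger readings.** A reader might infer that the table misstates background drugs generally, or that 'Others' would mostly repeat aminosalicylate and steroid use. The first fails because only the residual row is exposed. The second depends on prevalences the SAP does not give; 'Others' also takes in every remaining drug, antituberculosis drugs included, so the truly other share could be high.

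A reader might also infer that surgery will be under-reported. The SAP does not show this. It uses 'and' loosely elsewhere: responding patients are those rated improved and significantly improved; concomitant records are dropped if they ended before the first dose and began after the last; and the row titled chest X-ray and CT requires either. In both operation rows the patient-level rule that follows asks only for data corresponding to an operation. How far the tick box and the converted file overlap is unknown. What remains is an ambiguous condition that differs from the 'or' used for tick box and drug code in the previous-drug rows of 10.1.

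**Conclusion.** The 'Others' rule is wrong as written. It contradicts the section 11 class list, and the parallel rule for previously used drugs suggests an oversight. The direction is certain: the row can only be too high, and it is too high whenever at least one patient takes an aminosalicylate or steroid without a truly other drug. The amount cannot be computed from the SAP; the 6 to 48 points shown under independence rest entirely on assumed prevalences.

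The consequence is descriptive and confined to one row of Table 1.12.1. No test, safety rate or efficacy rate changes. The correction should be made because the printed figure would be wrong and the change is small.

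The operation point is secondary and conditional. It matters only if the joint condition is meant literally and some operations appear in one source alone.

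**What to change.** In SAP 10.1, row for concomitant drug (Others):

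- Exclude all six named classes by adding aminosalicylic acid preparation and steroid to the four already listed.
- Use one steroid label in 10.1 and 11, and state where non-oral steroids go so that each falls in exactly one class. Tables 2.9 and 3.4 list concomitant oral steroid as a tested factor, so the same definition should be used there.
- Change the closing clause to say that the remaining patients have no *other* concomitant drug.

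In the two operation rows of 10.1 (previous treatment and combination therapy), state the condition as box ticked *or* operation entry in the converted data, in line with the previous-drug rows. If the converted file is meant to adjudicate the box, keep 'and' but say so, and say which class a single-source record enters; 'or' would then count operations that the conversion had rejected.

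The cost is a few short edits to three rows of 10.1, the label in 11 if it changes, and the matching code. No new data are needed. The one decision that takes thought is the handling of non-oral steroids, which should be checked against the drug code list.
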